The NIH Toolbox is a multidimensional set of brief measures assessing cognitive, emotional, motor and sensory function from ages 3-85, meeting the need for a standard set of measures that can be used as a "common currency" across diverse study designs, including repeated measures designs, such as the present study. Specifically, we will use the NIH Toolbox Cognition Battery which is administered on an iPAD. The cognition battery consists of tests to assess Executive Function, Attention, Episodic Memory, Language, Processing Speed and Working Memory. Administering this battery will yield summary scores (i.e., Cognitive Function Composite Score and Crystallized Cognition Composite Score), as well as individual measure scores.

Rev Auditory Verbal Learning Test (RAVLT):

The RAVLT assesses verbal learning ability and memory; in this study, only learning ability is evaluated (4 minutes). A series of 15 words is presented to the participant 3 times via audio recording for standardization, and answers are recorded.

Stationary Postural Control/Force Plate:

Consistent with the methodology outlined by Campolettano et al., participants will complete two 30-second trials (one with eyes opened, one with eyes closed). Five measurements will be calculated at each time point (pre- and post-season): anterior-

posterior sway, medial-lateral sway, path length, maximum path velocity, and center of pressure area.

Vestibular/Ocular Motor Screening (VOMS):

The participant will be asked to complete a series of rapid head movements to assess five domains: smooth pursuit, saccades, near point convergence, vestibular ocular reflex, and visual motion sensitivity. Symptom provocation will be assessed by a trained member of the study team. Near point convergence will be averaged across three trials.

Conners' Continuous Performance Test (CPT) Third Edition (CPT-3):

Participants will complete a 14-minute computer-based assessment that evaluates selective, sustained and divided attention, as well as impulsivity and vigilance.

Triggers for Testing:

Triggers refer to the standards an athletic trainer or coach will use to determine whether or not an impacted player should receive further testing. The triggers for testing will be the standard already used by the athletic trainers and will not be altered due to this study. If a concussion is suspected, the athletic trainers typically use the SCAT5 on-field to determine whether to remove an athlete from play. Following removal from play, the athletic trainers use the SCAT5 to assist with a clinical diagnosis of concussion which would trigger further testing. Athletic trainers and physicians will follow normal methods for diagnosis and treatment of a concussion and not be restricted to only the information found in this protocol.

Post-Injury Testing:

Post-injury testing is any testing that is administered after a player has been diagnosed by a team physician or athletic trainer to have a concussion. The records for Post-Injury Testing will only be provided and used for research analysis AFTER a concussion has been diagnosed, pending signed authorization by the players on the Informed Consent document. No additional or different testing will be done because of a player's participation in the study.

Post-injury testing will include baseline cognitive, postural control, and vestibular/ocular motor testing within 24-48 hours after concussion diagnosis.

Outcome Measure(s)

- Primary Outcomes:
 - o Number of head impacts, impact rate
 - Mean and 95th percentile number of impacts, linear acceleration, rotational acceleration by session type, activity, skill and behavior
 - Pre- to Post-Season change scores for:
 - ImPACT
 - NIH Toolbox
 - RAVLT
 - Postural Control
 - VOMS
 - Conners' CPT
- Secondary Outcomes:
 - Implementation facilitators and barriers
 - Intervention fidelity
 - Adaptation of the intervention

Analytical Plan

Statistical analysis of biomechanical data will be based on our previous approaches.^{9,11,64} Head impact data will be transformed to the head center of gravity using Matlab (Mathworks, Inc., Natick, MA) and quantified for each session (i.e., practice or game) and practice drill category (i.e., conditioning, tackling) and across drill types (i.e., Oklahoma, one-on-one) in terms of mean number of impacts and impact rate and mean and 95th percentile head acceleration.

Descriptive statistics will be computed from survey responses using SAS. Field notes and recordings from focus meetings will be reviewed by reading transcripts and listening to recordings to identify recurrent themes, issues, and concepts and a thematic framework will be created surrounding the awareness and receptivity of the stakeholders to create a safer practice structure. Data will be indexed, charted, and mapped using a schematic diagram to guide interpretation of the results. Survey questions and responses will be grouped according to the thematic framework. Perceived feasibility (FIM), acceptability (AIM), and stakeholder survey constructs measured at the initial meeting (Aug) will be compared to the final meeting (Nov).

We will use established qualitative methods ^{104,105} to analyze field notes and recordings from stakeholder meetings to iteratively assess the nature of the evidence-based strategies, strengths, and weaknesses, while addressing the availability, acceptability, affordability, and potential barriers with each possible evidence-based strategy. Field notes and recordings from stakeholder meetings will be reviewed by reading transcripts and listening to recordings to identify recurrent themes, issues, and concepts for the creation of a thematic framework. ¹⁰³ Attitudes, practices, barriers, needs, and concerns will be categorized. Common themes will be grouped with the aforementioned categories or new categories will be created as themes emerge. Survey responses, transcriptions, and recordings will be indexed and charted based on the classifications identified in the thematic framework. These data will finally be mapped and interpreted to establish associations, explanations, and strategies that target the individual-, interpersonal-, and community-levels influencing behaviors affecting head impact exposure. These data will ultimately inform the development of the practice structure, implementation plan, and evaluation framework.

On-field head impact data for each athlete will be quantified for each practice or game by number of impacts, impact rate, mean, median, and 95th percentile of head acceleration, and location of impact. Impact rates and percentiles (i.e., 50th, 95th) computed from the distribution of accelerations will be compared between unexposed (year 2, published iTAKL and BRP study data^{61,106–108}) and exposed seasons of data collection. Mixed-effects models (in SAS) will be used to assess differences in head impact exposure in practices and games before (year 2, published iTAKL and BRP study data^{61,106–108}) and after the intervention, adjusting for confounding factors, including team. We will examine the consistency of intervention effects on exposure outcomes between teams and among players over time, with the goal of learning how to refine and tailor the intervention to increase adherence and potential effectiveness. Because this is a pilot study, we will lack sufficient power to fully test the effectiveness of the intervention; however, we will gather essential information for a future R01-supported randomized control trial.

All clinical assessment scores will be compared to same age peers at testing time (via published normative values) to control for developmental changes that may occur during the study period. Scores will be normalized (i.e. z-scores) to facilitate comparisons among cognitive tests. Kinematic metrics (i.e., total impacts, 95th percentile accelerations and rotational velocity, RWE) will be time-varying covariates in generalized linear and mixed effects models. The modeling framework, with its random effects structure, will allow for assessment of clinical outcome differences pre- to post-season over time between the intervention athletes and controls. We will also describe whether associations may vary according to athletes' characteristics.

Descriptive data and inferential statistics related to implementation facilitators and barriers (i.e., feasibility, acceptability), fidelity (i.e., extent to which the intervention was implemented as prescribed), and adaptation (i.e., changes) of the intervention will be analyzed. These data will be abstracted from standardized forms collected during on-field observations, video-analysis of practices and games, and brief surveys and field notes from stakeholder feedback meetings. Common themes will be grouped, and qualitative data indexed and charted. These data will be analyzed to assess the degree to which the practice structure was effective at reducing head impact exposure, was adopted by the youth football coaches, and to identify the key components of the strategy that may be implemented and sustained over time.

Human Subjects Protection

Subject Recruitment Methods

[name] will work with the league executive board to arrange meetings for coaches, parents, and players to describe the study and provide opportunities to answer questions. She and study personnel will also attend pre-season conditioning sessions to meet with parents, coaches, and athletes not present at the meetings. Those not present at the meetings or pre-season conditioning sessions will be sought out individually by phone for their interest in participating in the study. All interested athletes on these teams will be allowed to participate; of those enrolled, 15 children on each team will be randomly selected for instrumentation with head impact sensors using a random numbers table. Coaches and parents of the participating teams will be recruited to participate in separate focus groups and league officials will be prospectively recruited to participate in key informant interviews. A new set of football coaches and teams will be prospectively recruited and enrolled in the intervention portion of this study using similar recruitment strategies as the controls. Informed consent will be obtained from adults (coaches, parents, and league officials) and parents/legal guardians of all youth athletes and participating athletes will sign consent and assent forms.

To maintain a robust cohort of subjects, we will enroll all interested subjects from each team for possible participation in the study and randomly choose 15 per team for study at the start of the season. Participation will be monitored weekly; if an athlete has attended 50% or less of the practices or games within a 3 weeks, a new subject who enrolled prior to the start of the season will be randomly chosen for biomechanical data collection and given a sensor. We anticipate a possible attrition rate of 15% based on experience from our existing R01s. To ensure that sufficient participants are included, we will work closely with the local youth football league to identify and engage additional teams, if needed.

To reward all subjects for attending appointments to complete baseline, post-injury, and post-season evaluation procedures during the contact sport seasons, a gift card will be awarded, at all appointments, for the subject's additional travel and time to attend the procedures. See the table below for gift card compensation amounts.

Neurocognitive Testing	Dental Impressions + Head/Face Measurements	Neurocognitive Testing, Impressions, Head/Face	Dental +
		Measurements	

Pre-season/baseline	\$20	\$20	\$40
Post-injury	\$20	N/A	
Post-season	\$40	N/A	

To reward all stakeholders for attending all meetings, focus groups or key informant interviews, a gift card will be awarded, at all appointments, for the additional travel and time to attend the meetings. See the table below for gift card compensation amounts. To encourage participation, participants enrolled in the focus groups and key informant interviews will be entered into a raffle for four Wake Forest Football Tickets. All focus group and key informant interview participants enrolled in the study at the time of the raffle will be eligible to win. Winner will be selected using a random numbers table.

	Focus Groups	Key Informant Interviews	Stakeholder Meetings	Athlete Stakeholder Meetings
Compensation for each meeting	\$20	\$20	\$20	\$20
Number of meetings	4	2	18	4
Total compensation*	\$80	\$40	\$360	\$80

*if all meetings are attended

The gift card will be given to the subject at the time of the meeting. A record confirming receipt by the subjects of the gift card will be kept.

Informed Consent

Signed informed consent will be obtained from each subject. [name] and trained study personnel will work with the league executive board to arrange meetings for coaches, parents, and players to describe the study and provide opportunities to answer questions. She and trained study personnel will also attend preseason conditioning sessions to meet with parents, coaches, and athletes not present at the meetings. Those not present at the meetings or pre-season conditioning sessions will be sought out individually by phone for their interest in participating in the study.

Informed consent will be obtained from each subject by the members of the study staff that are not directly affiliated with the prospective football programs or athletic departments. The informed consent form will be presented in individual meetings to each prospective participant in detail. Players, parents, and coaches will be encouraged to ask questions and will be given the opportunity to have all questions answered. The prospective participants will be told their participation is completely voluntary and they will not be pressured into participation. During the consent process, the study staff will work to minimize the possibility of coercion or undue influence. It is estimated that the individual consent process will take approximately 15 minutes per participant. The prospective participants will be spoken to in a one-on-one manner in a conversation that will take place in private, away from the rest of the team to avoid the potential for peer pressure.

An anonymous survey will be distributed to parents, coaches and league officials. A cover letter will be included stating that completion of the survey indicates consent to participate. The identity of those who have completed the survey will not be known to the research team.

Lastly, stakeholder involvement will be voluntary and informed consent will be provided prior to the stakeholder discussions. Stakeholders will be aware of other stakeholders included in group discussions as discussions will be conducted face to face; however, their identity within the youth football league will remain anonymous.

Confidentiality and Privacy

Confidentiality will be protected by collecting only information needed to assess study outcomes, minimizing to the fullest extent possible the collection of any information that could directly identify subjects, and maintaining all study information in a secure manner. To help ensure subject privacy and confidentiality, only a unique study identifier will appear on the data collection form. Any collected patient identifying information corresponding to the unique study identifier will be maintained on a linkage file, store separately from the data. The linkage file will be kept secure, with access limited to designated study personnel. Following data collection subject identifying information will be destroyed, consistent with data validation and study design, producing an anonymous analytical data set. Video and biomechanics data will be stored for six years, or five years after the completion of the study, whichever is longer. Data access will be limited to study staff. Data and records will be kept locked and secured, with any computer data password protected. No reference to any individual participant will appear in reports, presentations, or publications that may arise from the study.

Prevent Biometrics creates one of the mouthguards used in this study. Some information is required to create an account to use Prevent, such as your name, email address, password, date of birth, gender, height, weight, and in some cases your mobile telephone number. We may also choose to provide other types of information, such as a profile photo, biography, country information, and community username. Athlete's name and email address will not be provided to Prevent Biometrics. We will use anonymous study identifiers and our generic study email to protect participant confidentiality with the Prevent Biometrics system. The Prevent Privacy Policy is provided in the appendix.

FITBIR

Data from the study may be submitted to the Federal Interagency Traumatic Brain Injury (FITBIR) informatics system. FITBIR is a computer system run by the National Institutes of Health that allows researchers studying traumatic brain injury to collect and share information with each other.

During and after the study, the researchers will send information to FITBIR. However, before they send it to FITBIR, they will remove information such as name, date of birth, and city of birth, and replace that information with a code number. FITBIR will not be able to contact participants

Data and Safety Monitoring

[name] and mentor, [name], will be responsible for the overall monitoring of the data and safety of study participants. Data analysis will be overseen and completed by [name] under the guidance of [name] and co-mentors. Only members of the research team overseen by [name] will receive the acceleration data from the mouthpieces and be required to interpret the data. Team medical personnel and coaches will not review or monitor head impact data. [name] will pilot test the intervention developed in this study and complete data analysis under the supervision of [name].

The Wake Forest School of Medicine Institutional Data Safety and Monitoring Board (I-DSMB) will provide independent oversight of methodology and conduct, biostatistics, and ethics of this study. The I-DSMB provides oversight for Wake Forest Baptist Health investigator-initiated, locally conducted clinical trials receiving NIH support. Members of the Wake Forest School of Medicine I-DSMB have expertise in clinical trial methodology and conduct, biostatistics, ethics, and clinical research. The I-DSMB will monitor participant safety, evaluate the progress of the study, review procedures for maintaining the confidentiality of data, and the quality of data collection, management, and analyses. The I-DSMB will have access to all study data, documents and progress information, and will be notified of all changes that are made to the protocol.

Reporting of Unanticipated Problems, Adverse Events or Deviations

Any unanticipated problems, serious and unexpected adverse events, deviations or protocol changes will be promptly reported by the principal investigator or designated member of the research team to the IRB and sponsor or appropriate government agency if appropriate.

References

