- Aim 2: Develop an evidence-based intervention to reduce head impact exposure in youth football practices, using a community-engaged approach.
- *Aim 3:* Pilot-test the evidence-based practice structure to reduce head impact exposure and mitigate changes in clinical outcomes in youth football.

We **hypothesize** that (a) determinants at the individual (athlete), interpersonal (team & coach), and community levels (built & social environment) of the social ecological model⁸⁴ may be identified and targeted to reduce head impact exposure in youth football practices, and (b) an evidence-based strategy to reduce head impact exposure in practices may be developed and pilot tested using a community-engaged approach. (c) The reduction in exposure will be associated with a lower rate of change in pre- to post-season clinical outcome measures and cognitive function scores.

Methods and Measures

Design

Two local youth football teams at the middle school level (ages 11-14) will be recruited to participate in this study. Informed consent and signed assent forms will be obtained from parents/legal guardians of participating youth football players. All interested football players on the 2 teams will be enrolled; of those enrolled, 15-20 per team (n=30-40 total) will be randomly selected for instrumentation with head impact sensors using a random numbers table. Head impact sensors embedded in a custom mouthpiece will be used to collect head impact exposure in conjunction with on-field video data for a season. These data will be used to inform guided discussions with stakeholders (parents, coaches, league officials). Using an audit and feedback approach (sharing biomechanical data with the stakeholders), we will facilitate semi-structured focus groups with the coaches (n=8) and parents (n=10) of the participating teams, and key informant interviews with league officials (n=8), to assess the awareness and receptivity to creating a safer practice structure. Participants will be asked to complete a series of cognitive, vestibular/ocular motor, and postural stability tasks pre- and post-season.

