An anonymous survey concerning knowledge, attitudes, and practices as well as the perceived needs, perceived benefits, capacity, and barriers to implementing efforts to improve head impact safety will be created and sent to coaches, parents, and league officials (n=153). Data will be combined with published literature to inform the development of an evidence-based intervention using a community-engaged approach. At the end of year 3, two youth football teams at the middle school level will be recruited to pilot test the intervention developed in this study. The football coaches of each team will be prospectively recruited and enrolled. Informed consent will be obtained from adults (coaches and parents/legal guardians of youth athletes) and parents/legal guardians of all participating youth athletes will sign assent forms. Again, all interested athletes on these teams will be enrolled; of those enrolled, 15-20 per team (n=30-40 total) will be randomly selected for instrumentation with head impact sensors using a random numbers table. Athletes will also complete the series of cognitive, vestibular/ocular motor, and postural stability tasks pre- and post-season. On-field activity, skills, and behaviors will be monitored with head impact sensors and on-field video data to evaluate the effectiveness of the intervention at reducing head impact exposure and the acceptability, feasibility, and fidelity of the intervention. The results will be disseminated to the youth football league at the end of the study.

Setting

Biomechanical data collection will occur during youth football practices and games. Stakeholder meetings and key informant interviews will be conducted at the local elementary school, community centers, and Biotech Place in Winston Salem, NC. Clinical outcome data collection and data analysis will be conducted at the WFU Center for Injury Biomechanics, a research lab located at Biotech Place. Additionally, we plan to recruit individuals across the Piedmont Triad and Charlotte Mecklenburg regions in Fall 2024 data collection.

Subjects selection criteria

• Inclusion Criteria

Mouthpiece and Clinical Outcome Data Collection:

All athletes participating on the prospective teams will be eligible for the study, including those with braces longer than 6 months.

Focus Groups, Key Informant Interviews:

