Former youth football players currently participating at the Varsity level of high school football (n=6) and collegiate level (n=6) will be invited to participate in separate (one for high school, two for collegiate) 60-minute discussions before the intervention (July), in the middle of the intervention/football season (October), after the football season (January), and upon completion of analysis of the results (May). The purpose of the stakeholder discussions is to assess the feasibility and potential utility of the implementation strategy and to further supplement our understanding of the intervention feasibility and acceptability. The Exploration, Preparation, Implementation, and Sustainment (EPIS)⁹⁷ conceptual model will be used to guide discussions. During the last 10 minutes of each discussion, participants will be asked to complete modified AIM and FIM surveys.⁸⁸ Questions 1 and 2 of the FIM surveys will be omitted for athlete stakeholders.⁹⁸ These surveys will be repeated at each meeting to determine changes in perceived acceptability and feasibility over time.

Neurocognitive Assessments:

Enrolled athletes may complete a series of clinical outcome assessments pre-and post-season, including measures of neurocognition, postural control, and vestibular/ocular motor symptoms. The parent and child versions of the *Behavior Rating Inventory of Executive Function (BRIEF) Monitoring Form*^{99,100} and *Revised Child Anxiety & Depression Scale (RCADS)*¹⁰¹ will be collected at the baseline and post-study assessments to monitor behavior and mood changes. The elements of the clinical outcome assessments are described below:

ImPACT:

For this study, the web-based version of the ImPACT (Immediate Post-Concussion Assessment and Cognitive Testing) will be given to athletes after diagnosis of a concussion. Administration of the test will be monitored by a member of the study staff member trained in the application of the ImPACT test. The ImPACT test takes approximately 20 minutes to complete.

NIH Toolbox:

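### ImPACT is a primary pre- to post-season change score, but its own test description schedules it only after a diagnosed concussion

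*Combined protocol and SAP*

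**What the plan says.** **Outcome Measure(s), Primary Outcomes.** Under "Pre- to Post-Season change scores for" the protocol names ImPACT, NIH Toolbox, RAVLT, Postural Control, VOMS and Conners' CPT, in that order.

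**Neurocognitive Assessments, ImPACT.** The paragraph says that in this study the web-based test "will be given to athletes after diagnosis of a concussion". It gives no other time and puts the duration at about 20 minutes.

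**Neurocognitive Assessments, opening paragraph.** "Enrolled athletes may complete a series of clinical outcome assessments pre-and post-season". The paragraph ends with "The elements of the clinical outcome assessments are described below", and ImPACT is the first element that follows.

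**Design.** "Participants will be asked to complete a series of cognitive, vestibular/ocular motor, and postural stability tasks pre- and post-season" and, for the intervention season, "Athletes will also complete the series of cognitive, vestibular/ocular motor, and postural stability tasks pre- and post-season". Neither sentence names a test.

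**Post-Injury Testing.** "Post-injury testing will include baseline cognitive, postural control, and vestibular/ocular motor testing within 24-48 hours after concussion diagnosis". Again no test is named.

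**Analytical Plan.** The mixed models are meant to allow "assessment of clinical outcome differences pre- to post-season over time between the intervention athletes and controls". They cover the clinical scores as a group, so ImPACT is included by implication.

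**The concern.** A pre- to post-season change score exists only for an athlete tested at both times. The one sentence that says when ImPACT is given describes a different occasion, triggered by a diagnosis, and in only some of the athletes.

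Two kinds of harm follow, depending on which text is wrong:

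- If the ImPACT paragraph is right, the plan names a primary outcome that cannot be formed. The only ImPACT data would come from concussed athletes. If such a score were used as the post-season value, it would reflect a recent concussion and not a season of exposure.
- If the outcome list is right, staff who work from the ImPACT paragraph will not collect the pre-season score, and it cannot be recovered once the season has started.

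In either case, a reader who later finds ImPACT sparse or absent in the results cannot tell whether that was planned, missed or selectively reported.

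**Working it through.** The plan gives no figure on this point to reproduce. The check sets every mention of ImPACT, and every general statement of assessment timing, side by side.

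**Step 1: what the outcome needs.** For athlete *i*, change*ᵢ* = post-season score*ᵢ* − pre-season score*ᵢ*. Both terms are required.

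**Step 2: what each text schedules for ImPACT.**

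| Section | Names ImPACT? | Timing |
|---|---|---|
| Outcome Measure(s) | Yes | Pre- and post-season, implied by a change score |
| ImPACT paragraph | Yes | After a concussion diagnosis |
| Neurocognitive Assessments, opening | No; ImPACT is the first element listed after it | Pre- and post-season, permissive wording |
| Design (two sentences) | No | Pre- and post-season |
| Post-Injury Testing | No | 24-48 hours after diagnosis |
| Analytical Plan | No | Pre- to post-season comparison |

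Only two places name ImPACT in the protocol body, and those two disagree.

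**Step 3: is the ImPACT paragraph unusual?** Of the other five instrument descriptions, the force-plate one states both season time points outright. The other four (NIH Toolbox, RAVLT, VOMS, Conners' CPT) give no time of their own, so the opening paragraph's pre- and post-season timing applies to them without contradiction. ImPACT alone has a time that differs from the battery's.

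**Step 4: count of usable pairs.**

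- ImPACT paragraph followed as written: 0 scheduled pre-season scores and 0 routine post-season scores, so 0 pairs. This holds for N = 30, N = 40 or any other N. No concussion rate is needed.
- Pre- and post-season reading: one pair for each athlete who completes ImPACT at both visits.

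**Step 5: extent.** Instruments listed: 6. Affected: 1. Unaffected: 6 − 1 = 5. The sample-size statement concerns correlations and the precision of a standard deviation at N = 30. It takes no input from ImPACT.

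**Step 6: testing time if both administrations must be added.** 2 × 20 minutes = 40 minutes per athlete per season.

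**The case against.** The strongest reply is that the ImPACT paragraph never says the test is given *only* after a concussion. It sits directly below a sentence presenting the tests as elements of a pre- and post-season battery, so the post-concussion administration could be an extra one. Two other places lean the same way. The compensation table in Subject Recruitment Methods pays for neurocognitive testing pre-season, post-injury and post-season. Post-Injury Testing describes its cognitive tests as baseline ones, which suggests a repeat of tests already given. The content of the timeline in Appendix 1 is not in the available text and could carry a schedule.

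Much of this stands. It makes pre- and post-season use plausible, perhaps the likelier intention, and it makes the zero-pair result conditional on one reading. It does not remove the conflict. None of these passages names ImPACT, the battery's opening sentence is permissive, and the ImPACT sentence has no word such as *also* to mark an added occasion. Staff who look up when to give ImPACT will find one answer, and it is not the one the outcome needs.

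It is also fair to say that this is a pilot which disclaims adequate power to test effectiveness, that no decision rule depends on ImPACT, and that three other cognitive tests remain. That limits the consequence. It does not make the named primary outcome computable under its own test description.

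**Conclusion.** The concern holds. The ImPACT paragraph and the primary outcome list cannot both be followed as written. Under the ImPACT paragraph there are 0 pre/post pairs and one named primary outcome cannot be computed. Under the pre- and post-season reading the outcome is sound, but the instruction to staff is wrong or incomplete. The documents do not show which was intended.

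The effect is limited to 1 of 6 change-score instruments and to the ImPACT part of the pre/post clinical models. The other five instruments, the head-impact outcomes and the sample-size statement stand.

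The conclusion rests on the available text, in which the Appendix 1 timeline has no visible content. It assumes nothing about how many athletes are concussed. Because a primary outcome is involved, the conflict should be resolved before any analysis.

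**What to change.** Decide which text is correct and make the others agree with it.

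- **(a) If ImPACT is given only after injury:** take it off the primary pre- to post-season list, state in the Analytical Plan that the pre/post clinical models exclude it, and report it descriptively as a post-injury measure. Cost: one line in Outcome Measure(s) and one clarifying sentence in the Analytical Plan. No extra data are needed.
- **(b) If ImPACT is given pre- and post-season:** correct the ImPACT paragraph to say so. If it is also given after injury, state that post-injury scores do not enter the change score. Cost: a sentence or two of wording. Only if the two tests are not already being given does this add about 40 minutes of testing per athlete per season.

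For seasons already completed, the text should record what was actually administered, so that any absence of ImPACT change scores is explained.
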